4.3.7 Day 37 (+/- 7 days)

- Obtain vital signs/ ECOG performance status
- Monitoring of concomitant medications
- Assessment of adverse events and toxicity grading according the CTCAE v4.0
- CBC with Differential, and platelet count
- Comprehensive metabolic panel
- Distribution of a 6-week supply of ibrutinib. Ibrutinib will be self-administered by subject daily.
- FNA of accessible tumor, if available, for research studies. If additional sites of disease are safely accessible via fine needle aspiration, these may be biopsied as well.
- Collection of 1 purple top tube for research correlates

- *Only for subjects with sufficient material from an excisional biopsy:* Apheresis for collection of peripheral blood mononuclear cells (PBMC) (approximately 2 hours) to provide adequate sample for research studies (+/- 10 days).
- *Only for subjects not undergoing apheresis:* Collection of 7 additional green top tubes of peripheral blood for research correlates (+/- 10 days).

4.3.8 Weeks 12, 24, 36, 48, 60, 72, 84 (+/- 10 days):

- History and physical examination
- Obtain vital signs/ ECOG performance status
- Monitoring of concomitant medications
- Assessment of adverse events and toxicity grading according the CTCAE v4.0
- Routine CBC, differential, and platelet count
- Routine Comprehensive metabolic panel
- LDH
- Distribution of ibrutinib. Ibrutinib will be self-administered by subject daily.
- Weeks 12, 24, 48, 72 only - Determination of response to treatment with CT scans of the chest/ abdomen/ pelvis or other medically appropriate imaging modality to evaluate all areas of disease followed by calculation of response by the Cheson Criteria (49) for lymphoma subjects (draining lymph nodes of the injected region will be excluded from this assessment, since SD-101 injections may cause transient enlargement of the draining lymph nodes). CT scan is the preferred mode of imaging, however, if a CT scan is contraindicated or if it is felt by the Sponsor Investigator that a PET/CT will be a better modality to assess a particular subject, a PET/CT may be used for evaluation.
- Collection of 1 purple top tube for research correlates
- *Optional:* If there is no evidence of disease on CT scan, a bone marrow biopsy will be obtained to document whether a complete response is achieved.
- At Week 12 only, 7 additional green top tubes of peripheral blood will be collected

4.3.9 Final Study Visit

Subjects who withdraw from treatment due to progressive disease will be seen within 4 weeks of the determination of progressive disease for a final visit. Subjects who withdraw due to intolerance of treatment should be followed weekly until all toxicities have reverted to Grade ≤ 2 or have stabilized in the opinion of the Investigator, at which point they will undergo the final visit. All subjects who withdraw for any reason other than progressive disease will be seen within 4 weeks of withdrawal for a final visit.

At the Final Study Visit, the following procedures will be performed:

- History and physical examination
- Obtain vital signs/ ECOG performance status
- Monitoring of concomitant medications
- Hematology: CBC with differential and platelet count
- Chemistry: comprehensive metabolic panel
- LDH
- Collection of 1 purple top tube for research correlates

- If not already radiologically documented within 4 weeks, determination of extent of disease with CT scans, or any other radiographic procedures determined appropriate by the investigator, followed by calculation of response by the Cheson criteria (49).
- If progressive disease, obtain an FNA of accessible tumor(s), if available, for research studies (optional).
- Collection of 7 green top tubes of peripheral blood for research correlates

4.4 Follow-Up Period

After Week 96, subjects will be evaluated every 3 to 6 months with CTs at intervals per standard practice at our institution, until disease progression or subject withdrawal.

4.5 Duration of Therapy

The planned duration of study for each subject is approximately 96 weeks, after which time the primary evaluation of safety, efficacy and immune response will be performed. Subjects will remain on study until development of disease progression, intolerable toxicity or any of the conditions outlined in Section 4.10 (Criteria for removal from study). Treatment toxicity will be evaluated at each study visit during the treatment period and at the final visit in Week 96. After Week 96, low-grade B-cell lymphoma subjects will be followed every 3 to 6 months as part of routine care until disease progression or subject withdrawal from the study.

4.6 Duration of Follow Up

After Week 96, subjects will be followed every 3 to 6 months as part of routine care until disease progression or subject withdrawal from the study. Subjects who withdraw from treatment due to progressive disease will be seen within 4 weeks of the determination of progressive disease for a final visit. Subjects who withdraw due to intolerance of treatment should be followed weekly until all toxicities have reverted to Grade ≤ 2 or have stabilized in the opinion of the Investigator, at which point they will undergo the final visit. All subjects who withdraw for any reason other than progressive disease will be seen within 4 weeks of withdrawal for a final visit.

4.7 Radiotherapy Administration

All subjects will receive 2 Gy radiation to a single tumor site on each of 2 consecutive days (Day 1 and Day 2).

4.8 Investigational Agent Administration: SD-101

The first injection of SD-101 will be performed on Day 2, within 12 hours of the radiation treatment. Subsequent injections of SD-101 will begin approximately one week later (Day 9), to be administered once per week for 3 weeks, for a total of five injections over a 4-week period.

SD-101 is supplied in individual vials at a concentration of 5 mg/mL or 16 mg/mL. Per instruction from Dynavax Pharmacy Manual (Dynavax Study DV3-MEL-01) below, SD-101 at 16 mg/mL will be diluted to a concentration of 5 mg/mL in normal saline prior to pharmacy dispensation.

SD-101 drug product should be removed from storage at 2° to 8°C and placed at ambient temperature prior to preparation for administration per the equilibration protocol below. Each vial of SD-101 drug product and prepared dose are for single-use only.

NOTE: SD-101 drug product or diluted SD-101 drug product is stable at room temperature for 8 hours. The SD-101 drug product or corresponding diluted SD-101 drug product must be used within 8 hours of removal of the SD-101 drug product vial from refrigerated storage. Prior to any drug preparation, prepare a clean working surface. Use aseptic technique to reduce the possibility of contamination, eg, wear gloves, use isopropyl alcohol to wipe down all vials (including rubber stopper area), etc. All syringes and sterile empty vials are for single-use; use only unopened syringes, needles, and/or vials for each step.

4.8.1. SD-101 DRUG PRODUCT EQUILIBRATION PROTOCOL:

Remove SD-101 drug product vial(s) from refrigerated storage. Allow SD-101 drug product to come to ambient temperature for 20 minutes. Gently mix SD-101 drug product by completely inverting vial(s) by hand and repeating 10 times.

NOTE: If diluent has been stored under refrigerated conditions, it must be allowed to come to ambient temperature for 20 minutes prior to preparation of the dosing solution.

4.8.2. PREPARATION OF SD-101 DOSING SOLUTION

All vials (SD-101 drug product, diluted SD-101 drug product, and diluent) are for single-use only. Prepare the appropriate dosing solution as specified below.

4.8.2.1 DILUTION & DOSE PREPARATION

Note: This section requires the use of 1 vial of 16 mg/mL SD-101 drug product. Draw **1.1 mL** of 0.9% sodium chloride diluent in a 3 mL syringe and transfer into an empty sterile mixing vial (2 or 5 mL capacity).

Note: While injecting the 0.9% sodium chloride diluent into the empty vial, ensure that pressure does not build up in the vial by equalizing the pressure recurrently. Draw **0.50 mL** from the SD-101 drug product vial (16 mg/mL) in a 1 mL syringe attached with a 20-25G needle, and transfer into the same sterile mixing vial containing the **1.1 mL** diluent. Mix the solution by gently inverting the vial completely 10 times. This mixing vial will contain a 5 mg/mL solution of SD-101.

FOR 3 mg DOSE: Using a 20-25G needle, draw **0.60 mL** of the diluted SD-101 drug product from the mixing vial into a 1 mL syringe for the administration of a 3 mg fixed dose of SD-101. **A 25-30G needle must be used to administer the dose of SD-101.**

FOR 1 mg DOSE: Using a 20-25G needle, draw **0.20 mL** of the diluted SD-101 drug product from the mixing vial into a 1 mL syringe for the administration of a 1 mg fixed dose of SD-101. **A 25-30G needle must be used to administer the dose of SD-101.**

The site of injection will be into an accessible enlarged lymph node or subcutaneous tumor site. Injections will be prepared and administered by a person designated by the principal investigator (eg, sub-investigators, study nurses) in response to written orders from the investigators.

4.9 Investigational Agent Administration: Ibrutinib

Subjects will begin treatment with ibrutinib on Day 10 of study treatment.

Ibrutinib is supplied as white opaque 140 mg capsules marked with “ibr 140” in black ink. Subjects will take 4 capsules daily for a total dose of 560 mg PO. The capsules should be swallowed intact and subjects should not attempt to open capsules or dissolve them in water. The use of strong CYP3A inhibitors/inducers, and grapefruit and Seville oranges should be avoided for the duration of the study.

If a dose is not taken at the scheduled time, it can be taken as soon as possible on the same day with a return to the normal schedule the following day. The subject should not take extra capsules to make up the missed dose.

Ibrutinib will be dispensed to subjects in bottles at designated visits. Unused ibrutinib dispensed during previous visits must be returned to the site and drug accountability records updated at each visit. Returned capsules must not be re-dispensed to anyone.

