Absorption: Ibrutinib is absorbed after oral administration with a median Tmax of 1 to 2 hours. Ibrutinib exposure increases with doses up to 840 mg. The steady-state AUC (mean \pm standard deviation) observed in subjects at 560 mg is 953 ± 705 ng·h/mL and in subjects at 420 mg is 680 ± 517 ng·h/mL. Administration with food increased ibrutinib Cmax and AUC by approximately 2 to 4- and 2-fold, respectively, compared with administration of ibrutinib after overnight fasting. Distribution: Reversible binding of ibrutinib to human plasma protein *in vitro* was 97.3% with no concentration dependence in the range of 50 to 1000 ng/mL. The volume of distribution at steady state (Vd,ss) was 683 L, and the apparent volume of distribution at steady state (Vd,ss/F) was approximately 10000 L.

Metabolism: Metabolism is the main route of elimination for ibrutinib. It is metabolized to several metabolites primarily by cytochrome P450, CYP3A, and to a minor extent by CYP2D6. The active metabolite, PCI-45227, is a dihydrodiol metabolite with inhibitory activity towards BTK approximately 15 times lower than that of ibrutinib. The range of the mean metabolite to parent ratio for PCI-45227 at steady-state is 1 to 2.8.

Elimination: Intravenous clearance was 62 and 76 L/h in fasted and fed conditions, respectively. In line with the high first-pass effect, the apparent oral clearance is approximately 2000 and 1000 L/h in fasted and fed conditions, respectively. The half-life of ibrutinib is 4 to 6 hours. Ibrutinib, mainly in the form of metabolites, is eliminated primarily via feces. After a single oral administration of radiolabeled [¹⁴C]-ibrutinib in healthy subjects, approximately 90% of radioactivity was excreted within 168 hours, with the majority (80%) excreted in the feces and less than 10% accounted for in urine. Unchanged ibrutinib accounted for approximately 1% of the radiolabeled excretion product in feces and none in urine, with the remainder of the dose being metabolites.

Renal Impairment: Ibrutinib is not significantly cleared renally; urinary excretion of metabolites is < 10% of the dose. Creatinine clearance > 25 mL/min had no influence on the exposure to ibrutinib. There are no data in subjects with severe renal impairment (CLcr < 25 mL/min) or in subjects on dialysis.

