Hepatic Impairment: Ibrutinib is metabolized in the liver. In a hepatic impairment trial, a single dose of 140 mg of ibrutinib was administered in non-cancer subjects. Ibrutinib AUC increased 2.7-, 8.2- and 9.8-fold, respectively, in subjects with mild (n = 6), moderate (n = 10) and severe (n = 8) hepatic impairment relative to subjects with normal liver function. Ibrutinib Cmax increased 5.2-, 8.8- and 7.0-fold, respectively, in subjects with mild, moderate and severe hepatic impairment relative to subjects with normal liver function.

Drug Interactions

Coadministration of Ibrutinib with CYP3A Inhibitors: In a sequential design trial of 18 healthy, fasted volunteers, a single dose of 120 mg of ibrutinib was administered alone on Day 1 and a single dose of 40 mg of ibrutinib was administered on Day 7 in combination with 400 mg of ketoconazole (given daily on Days 4 to 9). Ketoconazole increased ibrutinib dose-normalized Cmax and AUC 29-fold and 24-fold, respectively. Simulations using fasted conditions indicate that moderate CYP3A inhibitors diltiazem and erythromycin may increase AUC of ibrutinib by 5- to 8-fold.

Coadministration of Ibrutinib with CYP3A Inducers: PK data from a dedicated drug interaction trial showed that rifampin (a strong CYP3A inducer) decreases ibrutinib Cmax and AUC by more than 13- and 10-fold. Simulations using PBPK suggested that a moderate CYP3A inducer (efavirenz) may decrease the AUC of ibrutinib by up to 3-fold.

Efficacy of Ibrutinib in Follicular Lymphoma

Ibrutinib has been studied in the treatment of subjects with low-grade follicular lymphoma. In a phase 1 study of subjects with relapsed or refractory B-cell malignancies, 13 subjects with follicular lymphoma were evaluated for response to ibrutinib, with 7/13 subjects showing a >50% decrease in sum of the largest diameter of each target lesion (11). The MTD in this study was 560 mg daily and this dose showed full-target occupancy. Preliminary results from a phase 2 trial of ibrutinib monotherapy in relapsed/refractory follicular lymphoma showed an overall response rate of 30% in 40 subjects on the intention-to-treat analysis. An additional 14 subjects had reduction of tumor size not meeting response criteria (12).

Efficacy of Ibrutinib in Marginal Zone Lymphoma

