3.2 Exclusion Criteria

- 3.2.1 Autoimmune disease requiring treatment within the last 5 years including systemic lupus erythematosus, rheumatoid arthritis, multiple sclerosis, Sjögren's syndrome, autoimmune thrombocytopenia, uveitis, or other if clinically significant
- 3.2.2 Major surgery or a wound that has not fully healed within 4 weeks of enrollment.
- 3.2.3 History of stroke or intracranial hemorrhage within 6 months prior to enrollment.
- 3.2.4 Requires anticoagulation with warfarin or equivalent vitamin K antagonists.
- 3.2.5 Requires chronic treatment with strong CYP3A inhibitors.
- 3.2.6 Vaccinated with live, attenuated vaccines within 4 weeks of enrollment.
- 3.2.7 Known history of human immunodeficiency virus (HIV) or active Hepatitis C Virus or active Hepatitis B Virus infection or any uncontrolled active systemic infection.
- 3.2.8 Known CNS lymphoma.
- 3.2.9 Subjects with a history of prior malignancy with the exception of non-melanoma skin cancer, carcinoma in situ of the cervix, in situ carcinoma of the bladder, stage 1 prostate cancer that does not require treatment, or other malignancy that has undergone potentially curative therapy with no evidence of disease for the last > 2 years and that is deemed by the investigator to be a low risk for recurrence.

- 3.2.10 History of allergic reactions attributed to compounds of similar composition to SD-101 or ibrutinib
- 3.2.11 Treatment with an immunosuppressive regimen of corticosteroids or other immunosuppressive medication (eg, methotrexate, rapamycin) within 30 days of study treatment. Note: subjects may take up to 5 mg of prednisone or equivalent daily. Topical and inhaled corticosteroids in standard doses are allowed.
- 3.2.12 Significant cardiovascular disease (ie, NYHA class 3 congestive heart failure; myocardial infarction with the past 6 months; unstable angina; coronary angioplasty with the past 6 months; uncontrolled atrial or ventricular cardiac arrhythmias).
- 3.2.13 Pregnant or breast feeding.
- 3.2.14 Any other medical history, including laboratory results, deemed by the investigator to be likely to interfere with their participation in the study, or to interfere with the interpretation of the results.

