4.2 Informed Consent and Screening Period

Subjects who may be eligible for the trial will be approached by the Investigator and offered participation in the trial. The Investigator or co-Investigator will explain the study to the potential subject verbally, providing all pertinent information (purpose, procedures, risks, benefits, alternatives to participation, etc.), and will allow the potential subject ample opportunity to ask questions. Following this verbal explanation, the potential subject will be provided with the IRB approved informed consent form and will be afforded sufficient time to consider whether or not to participate in the research. After allowing the potential subject time to read the consent form, the investigator or approved designee (study coordinator) will answer any additional questions the potential subject may have and will obtain the subject's signature on the consent form. The investigator or designee will also sign the consent form. A signed copy of the consent form will be given to the subject, scanned into the medical record and distributed to the pharmacy and CTRU as per Stanford Cancer Clinical Trials Office (CCTO) Standard Operating Procedures. Before any protocol-specified procedures are conducted, each prospective participant must provide informed consent.

The screening period will take place up to 4 weeks prior to first dosing. Studies to evaluate the extent of tumor burden may be performed up to 6 weeks prior to dosing.

Subjects will undergo the following procedures during the screening period:

- Written informed consent
- Medical history and complete physical exam
- Obtain vital signs / ECOG performance status
- Monitoring of concomitant medications
- Hematology: CBC, differential, platelet count
- Chemistry: comprehensive metabolic panel
- LDH
- Urine pregnancy test (for females of childbearing potential)
- Determination of extent of disease with CT scans or PET/CT to evaluate all areas of known or suspected neoplastic disease. Procedures performed prior to subject entry into the trial, but within 6 weeks of first dosing, will fulfill the screening requirements.
- Infectious disease screening- HIV antibody testing, Hepatitis B surface antigen, Hepatitis B core antibody and Hepatitis C antibody testing

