4.10.2 Restricted Therapies

CYP3A Inhibitors

Use of a strong CYP3A inhibitor for more than 7 days is prohibited. If a moderate CYP3A inhibitor must be used, the dose of ibrutinib will be reduced by 140 mg daily. Avoid grapefruit and Seville oranges during ibrutinib treatment, as these contain moderate inhibitors of CYP3A. Subjects taking concomitant strong or moderate CYP3A inhibitors should be monitored more closely for signs of ibrutinib toxicity.

Surgeries and Procedures

The following guidance should be applied during the perioperative period for subjects who require surgical intervention or an invasive procedure while receiving ibrutinib:

For any planned surgery or invasive procedure requiring sutures or staples for closure, ibrutinib should be held at least 7 days prior to the intervention and should be held at least 7 days after the procedure, and restarted at the discretion of the investigator when the surgical site is reasonably healed without serosanguineous drainage or the need for drainage tubes.

For planned minor procedures (such as a central line placement, lymph node biopsy (not including fine needle biopsy), thoracentesis, or paracentesis) ibrutinib should be held for at least

3 days prior to the procedure and should not be restarted for at least 3 days after the procedure. For bone marrow biopsies that are performed while the subject is on ibrutinib, it is not necessary to hold ibrutinib for these procedures.

For emergency procedures, ibrutinib should be held after the procedure until the surgical site is reasonably healed, for at least 7 days after the urgent surgical procedure, or at the discretion of the investigator

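### No eligibility rule names hepatic impairment, although the protocol reports 8.2- to 9.8-fold ibrutinib AUC in moderate or severe cases; one exclusion line is a cheap safeguard

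*Combined protocol and SAP*

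**What the plan says.** Section 4.9 gives every subject the same ibrutinib dose from Day 10: "Subjects will take 4 capsules daily for a total dose of 560 mg PO".

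Section 2.2.2 (repeated in Section 5.2) describes metabolism, in the liver, as the main elimination route and reports the effect of liver disease: "Ibrutinib AUC increased 2.7-, 8.2- and 9.8-fold, respectively, in subjects with mild (n = 6), moderate (n = 10") and severe (n = 8). The data come from one 140 mg dose in non-cancer subjects. The same section reports from simulation that "moderate CYP3A inhibitors diltiazem and erythromycin may increase AUC of ibrutinib by 5- to 8-fold".

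Section 4.10.2 acts on the drug interaction in two ways: "If a moderate CYP3A inhibitor must be used, the dose of ibrutinib will be reduced by 140 mg daily", and "Subjects taking concomitant strong or moderate CYP3A inhibitors should be monitored more closely for signs of ibrutinib toxicity".

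For the liver, Section 3.1.6 limits AST/ALT to 3 x ULN and bilirubin to 1.5 x ULN, with bilirubin exceptions for Gilbert's syndrome and non-hepatic causes. Section 3.2.7 excludes active hepatitis B or C. Section 3.2.14 lets the investigator exclude for other history or laboratory results "deemed by the investigator to be likely to interfere with their participation in the study" or with interpretation of the results. Sections 3.1, 3.2, 4.9, 4.10 and 6.3 and Appendix A contain no rule that names hepatic impairment or a liver-function class.

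**The concern.** The protocol reports a large exposure effect of liver disease and attaches no named rule to it. It does act on two comparable pieces of pharmacokinetic information. A moderate CYP3A inhibitor triggers a dose cut and closer monitoring. Kidney function has an entry limit (creatinine clearance above 25 mL/min, Section 3.1.6d), although Section 2.2.2 says renal clearance of ibrutinib is not significant.

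Transaminases and bilirubin are indirect markers. No criterion uses ascites, encephalopathy, albumin, clotting or a liver class. A subject with impaired function but near-normal bilirubin and transaminases could therefore start the full dose unless the investigator uses 3.2.14. The stake is avoidable overexposure in a rare subject. The interruption rule in Section 6.3 and the DLT rules in Section 10.1.1 act only once toxicity has appeared; a screening criterion acts before the first dose.

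**Working it through.** The plan states no figure of its own on this point, so there is none to reproduce. The check compares reported effects and asks what dose would offset them.

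**Inputs**
- Planned dose: 4 x 140 = 560 mg (Section 4.9).
- Mean steady-state AUC (Section 2.2.2): "observed in subjects at 560 mg is 953" ng·h/mL (SD 705); 680 at 420 mg (SD 517).
- AUC fold change (Section 2.2.2): mild 2.7, moderate 8.2, severe 9.8; moderate CYP3A inhibitor 5 to 8.

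**Assumption.** Single-dose fold changes carry over to steady state, and exposure is proportional to dose. The protocol's means are roughly consistent with proportionality: 680/953 = 0.71 against 420/560 = 0.75.

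**Step 1: compare the effects at equal dose.**
- Against the top of the CYP3A range: 8.2/8 = 1.03 (moderate) and 9.8/8 = 1.23 (severe).
- Against the bottom: 8.2/5 = 1.64 and 9.8/5 = 1.96.

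Moderate impairment is about equal to the top of the CYP3A range; severe impairment is above it. Mild impairment, at 2.7, is below the whole range and is not part of this point.

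**Step 2: exposure relative to 560 mg with normal liver function.** Relative exposure = fold x dose/560. Parity dose = 560/fold.

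| Situation | 560 mg | 420 mg | 140 mg | Parity dose |
|---|---|---|---|---|
| Moderate impairment | 8.2 | 6.15 | 2.05 | 68 mg |
| Severe impairment | 9.8 | 7.35 | 2.45 | 57 mg |
| Moderate CYP3A inhibitor | 5 to 8 | 3.75 to 6.0 | 1.25 to 2.0 | 112 to 70 mg |

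In absolute terms, the estimated mean AUC at 560 mg is 953 x 8.2 = 7,815 in moderate and 953 x 9.8 = 9,339 ng·h/mL in severe impairment.

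**Step 3: can a dose cut do the job?** Section 4.9 requires 140 mg capsules to be swallowed intact, so 140 mg is the smallest daily step. At that step, exposure is still about 2.05 to 2.45 times the usual 560 mg exposure. The one-capsule cut of Section 4.10.2 leaves 6.15 to 7.35 times.

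**Step 4: how many subjects?** The documents give no prevalence and do not define the impairment classes, so the share that existing limits already exclude could be anything from none to nearly all. For scale, if 1% of otherwise eligible candidates were affected, the rule would touch 21 x 0.01 = 0.21 to 30 x 0.01 = 0.30 subjects.

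**The case against.** The strongest reply is that existing rules largely handle this. The liver laboratory limits, the viral hepatitis exclusion, ECOG 0 or 1 and life expectancy over 4 months leave little room for moderate or severe liver disease. Criterion 3.2.14 would let an investigator exclude known cirrhosis or decompensation. A metabolic panel is repeated on Day 9, before the first ibrutinib dose, and Section 4.11 allows removal for an intercurrent condition or in the subject's best interests without waiting for toxicity. All of this stands. It makes entry unlikely, but it leaves the decision to discretion in a case the protocol's own data single out.

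A second reply is that the sources differ: a fasted simulation for CYP3A, and a small single-dose trial in non-cancer subjects for the liver. That also stands, and is why the comparison should not be pressed beyond being similar or larger.

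A reader might go further and infer that the CYP3A rule sets an accepted exposure ceiling (AUC at 420 mg times 5 to 8) that hepatic impairment breaches by a wide margin. The documents do not support this. The protocol sets no AUC limit. Section 4.10.2 bars strong inhibitors only beyond 7 days, although Section 2.2.2 reports a 24-fold AUC rise with ketoconazole and Section 4.9 says to avoid strong inhibitors. Much of the apparent excess would come from comparing 560 mg with 420 mg.

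Parity with 560 mg is likewise the yardstick used here, not the protocol's: its CYP3A cut does not restore parity either.

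**Conclusion.** The point holds as a cheap, low-frequency safety improvement. It is not an error in the plan. The protocol reports an 8.2- to 9.8-fold AUC rise in moderate or severe hepatic impairment, names no rule for it, and does act on a similar or smaller CYP3A effect. Existing limits make entry improbable without expressly preventing it.

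The size rests on fold changes from 10 and 8 non-cancer subjects and on linear carry-over to steady state. The number of subjects affected cannot be derived from the documents.

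A reader might also infer that a new on-study hold-and-restart rule is needed. The documents do not support that. Section 6.3 already provides for interruption for toxicity and Section 4.11 for removal. Grading liver function on study would also need examinations not scheduled on Days 9, 23 or 37, and a further hold rule would raise an unanswered question about DLT evaluability. Sample size, power and error rates are unaffected.

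**What to change.** Add one exclusion to Section 3.2 and the same line to Appendix A:

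*Known or clinically evident moderate or severe hepatic impairment, judged at screening from medical history, physical examination (eg, ascites, encephalopathy, jaundice of hepatic origin) and the metabolic panel.*

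The sponsor should name the grading scale, because Section 2.2.2 does not say which one defined the classes. Mild impairment should stay eligible, and Section 6.3 needs no change.

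Exclusion is a judgement, preferred to a reduced dose because even one capsule would leave roughly twice the usual exposure, on sparse single-dose evidence.

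The cost is one line in two places. Section 4.2 already schedules "Medical history and complete physical exam" and a comprehensive metabolic panel, so no new test is required. The downside is that a very small number of subjects become ineligible and the results will not extend to moderate or severe hepatic impairment.
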